10.1 Institutional Review Board

For every study site, only when the trial protocol is approved by the institutional review board, the enrollment of participant will begin.

10.2 Funding

This study was supported and funded by 2019 National Administration of Traditional Chinese Medicine “Project of building evidence-based practice capacity for TCM-Project BEBPC-TCM” and Guang'anmen Hospital, China Academy of Chinese Medical Sciences. The funder will not interfere the data collection, analysis, and interpretation; nor in the finishing of the manuscript, and decision to submit the manuscript for publication.

10.3 Compliance Improvement

- (1) Participants should participate in the trial voluntarily, and sign the informed consent.
- (2) Research assistants should record the participants' contact information in detail for the convenience of follow-up.
- (3) Before randomization, researchers should inform the participants that all the cost related to the examination and treatment would be exempted.
- (4) Each participant's participation in the trial should be taken charge of by the same research assistant and outcome assessor throughout the trial. They will explain the contents of notebook to participants, if necessary, remind the participants of their schedule by phone or we-chat, and instruct participants to complete the notebook.
- (5) For participants who have less compliance, we will still follow them up to record outcome measurements through phone or message.

10.4 Data Management

10.4.1 The Raw Data Management and Archiving

The Remote Data Capture (RDC) system will be used to perform data entry. The research assistants will fill out all the electronic Case Report Forms (eCRFs) through RDC system. Researchers will inspect the eCRF, and sign electronically for the eCRF going into effect. The eCRF and the trace of eCRF revising will be left in the Oracle database.

10.4.2 Data Entry and Storage

10.4.2.1 Database Building and Testing, Data Entry Interface

The data entry interface will be in accordance with the paper-version CRF. After preliminarily setting up the database, the entry clerks will input some analog data according to the CRF to test the database. The testing contains: (1) the agreement of the data entry interface and the paper version CRF; (2) the agreement of the exported data from the database and the analog data; (3) the agreement of the structure of the exported database and the paper-version CRF. After the testing, data administrators should revise the database and make a testing report. Then they electronically signed on the approval page of the database to indicate that the testing is completed. The electronic files of the analog CRF, noted CRF, screenshot of the data entry interface, database testing report, and the approval page of the database should be saved. If the database updates during the trial, the

electronic files mentioned above will also need to be updated.

10.4.2.2 Data Entry and Inspection

The research assistants take charge of the data entry for our trial. Before the entry, all the research assistants will accept the related training according to the data entry handbook. Researchers will inspect the database, and then sign electronically to let the data go in to effect.

10.4.3 Data Verification and Problems Solving

Researchers will verify the data through Data Verification Plan (DVP) approved by the data administrator and the statisticians. Data queries will be inputted to a data query database, and form the Data Clarification Form (DCF). After being inspected, the DCF will then be handed back to the original site, and the researchers of the site should answer the queries. Any revision of the database will be recorded through the RDC software.

10.4.4 Medical Coding

A data administrator who has the medical background is responsible for the medical coding. The coding contents include the clinical history, AEs, and combined medication use if any. The clinical history and AEs will be coded through MedDRA dictionary (Version 13.0), and the combined medication use will be coded via the Anatomical Therapeutic Chemical Classification (ATC).

10.4.5 Data Management Report

Data management report contains the aspects as followed: (1) name of the project; (2) members of the project; (3) actual first entry and finish time of every site; (4) problems and solutions during data management (if have any); (5) reconstruction of the database (if have any); (6) distribution of the participants; (7) participants who violate the trial protocol; (8) classifying plan of the statistical analysis population.

10.4.6 Data Auditing and Blinding Review

When the data checking is finished, a data auditing and blinding review meeting will be held. In the meeting, the data administrators, statisticians, researchers, clinical inspectors, and other related members will have a discussion on the following items according to the data management report and the data lists:

- Distribution of the participants;
- Protocol violation;
- Possible outlier;
- Baseline data;
- Outcomes;
- Statistical analysis plan.

Participants will be classified to their suitable statistical analysis sets according to the definition in the protocol. No patient can be excluded from the analysis, unless getting the permission of the meeting participants. All the meeting participants will sign the data locking consent, and the data auditing resolution.

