6.1 Randomization

Patients who provide informed consent and are eligible will be randomly assigned at a ratio of 1:1 to either the acupuncture group or the SA group using a central randomization system. The randomization scheme will be generated by Linkerm Pharm Technology Co., Ltd (Beijing, China) using statistical analysis software SAS 9.4 with “proc plan” program. The randomization sequence will be generated in varying block sizes and stratified by center. A comprehensive document describing the randomization scheme will be sealed in opaque envelopes by the staff who produce it and kept by another staff who takes no part in the clinical trial. The randomization scheme will not be checked by anyone except the senior system administrator. In each clinical center, a research assistant who takes no part in the treatment and outcome assessment will log in the web-based central randomization system to assess the random number and group allocation. All randomization will be masked until all data analyses have been conducted.

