11.1 Sample Size Calculations

A sample size of 196 participants (98 in each group) was estimated to have provide at least 80% power at a 2-sided significance level of 5% to detect on a between-group difference of 2.5 points in the RMDQ score [23], assuming a standard deviation of 5.5 and a 20% dropout rate.

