11.2 Statistical Analysis

Details of the pre-specified statistical analyses can be found in the Statistical Analysis Plan (SAP). Prior to database lock and before code breaking, a final version of the SAP shall be issued and approved by the study statistician, and the principal investigator. The SAP will define all “pre-specified, planned analyses” and provide the general specifications for the analysis of the data to be collected and presented in the Clinical Study Report.

12. References

1. Genevay S, Atlas SJ: **Lumbar spinal stenosis**. *Best Pract Res Clin Rheumatol* 2010, **24**(2):253-265.
8. Atlas SJ, Delitto A: **Spinal stenosis: surgical versus nonsurgical treatment**. *Clinical orthopaedics and related research* 2006, **443**:198-207.

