6.2 Statistical Analysis Set

The efficacy analyses will be done on the intention-to-treat (ITT) population, which will include all participants who will be randomized according to randomized treatment assignment. The safety analysis will be done on the safety population, which will include the ITT participants who received any treatment.

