6.3.4 Analyses for Secondary Outcome

Efficacy analyses for all secondary outcomes will be performed in the ITT population, without imputation of missing data.

The same approach for the primary outcome will be used in other continuous outcomes such as SSSQ for symptom severity, physical function. Categorical data will be compared between groups using a generalized linear model with a binomial distribution and identity link that will include the same covariate as the MMRM model. In addition to the proportion of participants who were somewhat satisfied and very satisfied based on the satisfaction domain of the SSSQ, we will be analysis use the generalized linear model with the same covariate as the MMRM model. Patients' expectations of acupuncture for general disease and for DLSS, blinding, adherence data will present for descriptive purposes only.

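### Protocol 10.4.6 lets the pre-lock review meeting permit exclusions from an unnamed analysis without criteria, which conflicts with the all-randomised efficacy set in SAP 6.2 and 6.3.4

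*Combined protocol and SAP*

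**What the plan says.** Protocol 10.4.6 sets up a data auditing and blinding review meeting once data checking is finished. Data administrators, statisticians, researchers, clinical inspectors and other related members attend. They discuss the distribution of participants, protocol violations, possible outliers, baseline data, outcomes and the SAP. Two sentences then govern the analysis sets. One ties classification to definitions made elsewhere: "Participants will be classified to their suitable statistical analysis sets according to the definition in the protocol". The other deals with leaving patients out, and makes that depend on the meeting's consent: "No patient can be excluded from the analysis, unless getting the permission of the meeting participants".

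Protocol 10.4.7 makes database lock conditional on an approved classification plan and on a final SAP draft approved by the project leader. Protocol 11.2 refers to the SAP for the analyses and requires its final version to be approved before lock and before code breaking.

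SAP 6.2 bases efficacy on the ITT population, "which will include all participants who will be randomized according to randomized treatment assignment". Its only other set is the safety population, meaning ITT participants who received any treatment. SAP 6.3.4 adds: "Efficacy analyses for all secondary outcomes will be performed in the ITT population, without imputation of missing data". SAP 6.3.3 does not restate the population for the primary analysis, so 6.2 governs it.

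**The concern.** The sentence in 10.4.6 is phrased as a prohibition, but its exception has no limits. Any randomised patient may be left out of the analysis if the meeting agrees. The section gives no grounds and no decision rule, and does not say which analysis is meant. The meeting decides after seeing violations, outliers and outcomes, all of which arise after randomisation. An exclusion made that way would break the ITT comparison that the SAP promises for the primary outcome. Someone following 10.4.6 and someone following SAP 6.2 could therefore disagree on whether a given patient belongs in the primary analysis.

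There is also a smaller fault. Section 10.4.6 relies on definitions in the protocol, but the supplied protocol text contains none. Section 10.4.5 only lists a "classifying plan of the statistical analysis population" among the contents of a report, and section 11 refers to the SAP. The definitions are in SAP 6.2.

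**Working it through.** **1. The texts compared.**

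| Question | Protocol 10.4.6 | SAP 6.2 and 6.3.4 |
|---|---|---|
| Which analysis? | Not named | Efficacy: all randomised; safety: those who received any treatment |
| May a randomised patient be left out of efficacy? | Yes, if the meeting permits | No provision for it |
| Criteria | None; the list is an agenda | Membership follows from the definition alone |
| Is there a set for discretionary exclusions? | Not stated | No per-protocol or modified set is defined |

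**2. Design values.** Protocol 11.1 gives 98 per group, a 2.5-point difference, two-sided 5%, at least 80% power, "assuming a standard deviation of 5.5 and a 20% dropout rate". The normal approximation is n = 2(1.960 + 0.842)² × 5.5² / 2.5² ≈ 76 per arm, and 76/0.8 = 95. The t-test needs 77 per arm, and 77/0.8 = 96.25, so 97 per arm or 194 in total, close to the stated 196. With 20% lost, 98 × 0.8 = 78.4. At 78 per arm, t-test power is 0.805, so the stated figure is sound.

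**3. Masked removal, equal variances.** The set-up is normal change scores, SD 5.5, 78 per arm (156 pooled) and a two-sample t-test as a stand-in for the week-6 contrast of the mixed model for repeated measures (MMRM). The k worst changes, or the k most extreme in either direction, are removed without regard to arm. There were 60,000 simulations per cell.

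| k removed | Type I, worst | Type I, extreme | Shrinkage of a true 2.5, worst | Shrinkage of a true 2.5, extreme |
|---|---|---|---|---|
| 2 | 0.048 | 0.052 | 0.16 | 0.20 |
| 3 | 0.049 | 0.051 | 0.23 | 0.27 |
| 5 | 0.050 | 0.049 | 0.33 | 0.40 |
| 8 | 0.049 | 0.051 | 0.45 | 0.57 |

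As a share of 2.5, the shrinkage runs from 0.163/2.5 = 7% to 0.568/2.5 = 23%. A check on the bounded 0–24 scale with baseline adjustment (assumed baseline mean 13, SD 4, minimum 7) gave 6% to 20%.

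**4. Masked removal, unequal variances.** The set-up is no true difference, assumed SDs of 6.5 and 4.5, and removal of the worst 5 pooled changes. Most of those removed come from the more variable arm, so its mean improves. Repeated runs gave a shift of 0.59 to 0.61 points and type I error of 0.11 to 0.12. Removing the 5 most extreme in either direction gave no shift and type I error of about 0.06.

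**5. Violations that differ by arm.** If k of the 98 in one arm are excluded and their mean change differs by d from the rest, that arm's mean shifts by k × d / 98. With k = 5 and d = 5 (both assumed), 25/98 = 0.26 points, or about 10% of 2.5. Nobody needs to know the allocation for this to happen.

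**The case against.** The strongest defence is that a conforming reading exists. The default is no exclusion, the sentence before it ties classification to definitions, and the only sets defined are all randomised and all treated. Read with Protocol 11.2, the meeting could then remove people only from the safety set. There are procedural safeguards too. The classification plan and the SAP must be approved before lock, attendees sign a resolution, and Protocol 6.1 states "All randomization will be masked until all data analyses have been conducted".

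Part of this stands. The safeguards mean that any exclusion would be documented and agreed before lock, and Protocol 11.2 points to the SAP as the governing text. But the safety-set reading is strained: SAP 6.2 already removes untreated patients by definition, so no permission is needed, and the sentence says simply the analysis. Protocol 11.2 also does not say that the SAP overrides 10.4.6.

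It is also fair to object that nothing in the plan says outliers or poor responders will be removed; they are agenda items. A reader might infer that the sponsor intends to drop such patients. The documents do not support that.

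A reader might further infer that a few exclusions would take the trial below its stated 80% power. An unadjusted t-test gives 0.795 at 76 per arm, but SAP 6.3.3 plans a baseline-adjusted MMRM. Taking 5.5 as the unadjusted SD and assuming a baseline–change correlation of 0.2, 0.3 or 0.4, power at 76 per arm is 0.811, 0.831 or 0.859. That inference is not established.

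**Conclusion.** The inconsistency is real and concerns the primary analysis population. Protocol 10.4.6 permits discretionary exclusion without criteria, while SAP 6.2 and 6.3.4 leave no room for it. It should be corrected before the review meeting. The reference to definitions in the protocol is a minor cross-reference fault: the definitions exist, in SAP 6.2, and their absence from the protocol can be stated only for the supplied text.

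The size depends on assumptions. With a masked review and equal variances, type I error stays near 0.05 and the harm is a diluted effect (7% to 23% for 2 to 8 removals of 156). It would be wrong to infer from this that masking makes the clause harmless. With unequal variances or arm-related violations, masked exclusions can favour one arm, illustrated by a shift of about 0.6 points with type I error of 0.11 to 0.12. The removal counts, the SDs of 6.5 and 4.5, and the t-test stand-in are assumptions, not forecasts. No shortfall against the stated 80% power is claimed for the planned MMRM.

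**What to change.** In Protocol 10.4.6:

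1. Replace the permission sentence with: *All randomised participants remain in the ITT efficacy set in their randomised group and none may be removed; the meeting only assigns participants to the sets defined in SAP 6.2.*
2. Change the reference to the protocol's definition into a reference to SAP 6.2.
3. State that anyone who knows the allocation takes no part in classification.

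This is a wording amendment. It needs no extra data, participants or analyses, and the SAP does not change. Item 3 requires knowing who holds the allocation, and Protocol 5.3, 6.1, 6.2 and 10.5 do not agree on who randomises and who knows it. That conflict is a blinding matter, to be raised and reconciled as a separate point.

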10.4.7 Database Locking

The database will be locked if it fulfills all the aspects as followed: All the queries have been solved, and the database has been updated; No query has been found through the data inspection; The medical coding has been completed; The plan of the participants' classification has been approved; The final draft of the statistical analysis plan (SAP) has been made, and approved by the project leader.

The statisticians and the data administrators will sign the data locking form, and then the database will be locked. The locked database will be sent to the statisticians for further statistical analysis through the data format of SAS.

10.5 Quality Control

(1) To guarantee the quality of the study, the trial protocol will be reviewed and revised by expert acupuncturists, orthopedist, and statisticians several times.

(2) A central randomization system will be adopted to avoid selection bias.

(3) Strict eligible criteria will be pre-set to restrict the research population. The diagnosis, inclusion and exclusion criteria are designed in accordance with the guidance of NASS.

(4) Trial-specific (standardized operation procedure) extensive training will be given to all the research staff participating the trial at the project launching session. Acupuncturists will be trained on how to use the central randomization system, the standardized manipulation method, and needling rituals.

Outcome assessors will be trained how to fill the case report form. Clinical Research Assistants (CRC) will be trained to use data entry system.

(5) We will provide a self-assessment questionnaires/scales notebook for each participant. Participants will be asked to complete the notebook. During 6-week treatment period, participants will bring the notebook to hospital themselves. For the outcome assessment at weeks 18 and 30, they can mail the notebook to hospital or bring the manual to hospital themselves. The data from the notebook will be the raw data for analysis, and will be checked and recorded in CRF by outcome assessors. The double-input method will be used for data entry, and all data related to patients will be stored confidentially. The statistical analysis of the data will be calculated by independent statisticians. The participants, outcome assessors, CRC and statisticians will all be unaware of the group allocation.

(6) Participation processes in the trial of the same participants should be taken charge of by the same acupuncturist, research assistant and outcome assessor throughout the trial.

(7) A 3-level monitoring system will be established to periodically assess the performance of the trial: Level 1, Inspection; Level 2, Supervision; Level 3, Audit. Inspection: The investigator of each center will designate at least one researcher who take no part in the intervention to conduct a quality review of the center; Supervision: for each center, the study organizer (Guang'anmen Hospital, China Academy of Chinese Medical Sciences) will designate at least three researchers who take no part in the intervention to monitor the quality of the studies of that center; Audit: Linkermed Pharm Technology Co., Ltd will designate at least five quality control personnel to conduct a quality audit of the research.

11. Statistical consideration

11.1 Sample Size Calculations

A sample size of 196 participants (98 in each group) was estimated to have provide at least 80% power at a 2-sided significance level of 5% to detect on a between-group difference of 2.5 points in the RMDQ score [23], assuming a standard deviation of 5.5 and a 20% dropout rate.

11.2 Statistical Analysis

Details of the pre-specified statistical analyses can be found in the Statistical Analysis Plan (SAP). Prior to database lock and before code breaking, a final version of the SAP shall be issued and approved by the study statistician, and the principal investigator. The SAP will define all “pre-specified, planned analyses” and provide the general specifications for the analysis of the data to be collected and presented in the Clinical Study Report.

12. References

1. Genevay S, Atlas SJ: **Lumbar spinal stenosis**. *Best Pract Res Clin Rheumatol* 2010, **24**(2):253-265.
8. Atlas SJ, Delitto A: **Spinal stenosis: surgical versus nonsurgical treatment**. *Clinical orthopaedics and related research* 2006, **443**:198-207.

Appendix 2 Outcome Assessment Tools

List of the outcome assessment tools:

Modified Roland-Morris Disability Questionnaire (RMDQ)

Numerical Rating Scale (NRS)

Swiss Spinal Stenosis Questionnaire (SSSQ)

Hospital Anxiety and Depression Scale (HADS)

Expectation Assessment

Modified Roland-Morris Disability Questionnaire (RMDQ)

When your back or leg hurts, you may find it difficult to do some things you normally do.

This list contains sentences that people have used to describe themselves when they have back or leg pain. When you read them, you may find that some stand out because they describe you today. As you read the list, think of yourself today. When you read a sentence that describes you today, put a tick against it. If the sentence does not describe you, then leave the space blank and go on to the next one. Remember, only tick the sentence if you are sure it describes you today.

[figure not shown]
1. I stay at home most of the time because of my back problem or leg pain.
2. I change position frequently to try and get my back or leg comfortable.
3. I walk more slowly than usual because of my back problem or leg pain.
4. Because of my back problem or leg pain, I am not doing any of the jobs that I usually do around the house.
5. Because of my back problem or leg pain, I use a handrail to get upstairs.
6. Because of my back or leg, I lie down to rest more often.
7. Because of my back problem or leg pain, I have to hold on to something to get out of an easy chair.
8. Because of my back problem or leg pain, I try to get other people to do things for me.
9. I get dressed more slowly than usual because of my back problem or leg pain.
10. I only stand for short periods of time because of my back problem or leg pain.
11. Because of my back problem or leg pain, I try not to bend or kneel down.
12. I find it difficult to get out of a chair because of my back problem or leg pain.
13. My back or leg is painful almost all the time.
14. I find it difficult to turn over in bed because of my back problem or leg pain.
15. My appetite is not very good because of my back problem or leg pain.
16. I have trouble putting on my socks (or stockings) because of the pain in my back or leg.
17. I only walk short distances because of my back or leg back.
18. I sleep less well because of my back or leg problem.
19. Because of my back or leg pain, I get dressed with help from someone else.
20. I sit down for most of the day because of my back problem or leg pain.
21. I avoid heavy jobs around the house because of my back problem or leg pain.
22. Because of my back or leg pain, I am more irritable and bad tempered with people than usual.
23. Because of my back or leg pain, I go upstairs more slowly than usual.
24. I stay in bed most of the time because of my back or leg.

The score is the total number of items checked—i.e., from a minimum of 0 to a maximum of 24.

[figure not shown]
buttocks and/or legs or back average pain measured by Numerical Rating Scale (NRS)

The average pain scores for the buttocks and/or legs when walking, standing, or extending the back in the previous 1 week

(The degree of pain in the bilateral legs may be different, and data collection will be based on the degree of pain in the leg with more severe pain)

The average pain scores for the lower back when walking, standing, or extending the back in the previous 1 week

Swiss Spinal Stenosis Questionnaire (SSSQ)

Table 1. Component Items of the Symptom Severity Scale with Preoperative Responses

In the last month, how would you describe:	
1. The pain you have had on average including pain in your back, buttocks and pain that goes down the legs?	 1 None  2 Mild  3 Moderate  4 Severe  5 Very severe
2. How often have you had back, buttock, or leg pain?	 1 Less than once a week  2 At least once a week  3 Everyday, for at least a few minutes  4 Everyday, for most of the day  5 Every minute of the day
3. The pain in your back or buttocks?	 1 None  2 Mild  3 Moderate  4 Severe  5 Very severe
4. The pain in your legs or feet?	 1 None  2 Mild  3 Moderate  4 Severe  5 Very severe
5. Numbness or tingling in your legs or feet?	 1 None  2 Mild  3 Moderate  4 Severe  5 Very severe
6. Weakness in your legs or feet?	 1 None  2 Mild  3 Moderate  4 Severe  5 Very severe
7. Problems with your balance?	 1 No, I've had no problems with balance  3 Yes, sometimes I feel my balance  5 Yes, often I feel my balance is off, or that I am not sure-footed

Table 2. Component Items of the Physical Function Scale (Before Surgery)

In the last month, on a typical day:	
8. How far have you been able to walk?	 1 Over 2 miles

	 2 Over 2 blocks, but less than 2 miles
	 3 Over 50 feet, but less than 2 blocks
	 4 Less than 50 feet
	 1 Yes, comfortably
9. How you taken walks outdoors or in malls for pleasure?	 2 Yes, but sometimes with pain
	 3 Yes, but always with pain
	 4 No
	 1 Yes, comfortably
10. Have you been shopping for groceries or other items?	 2 Yes, but sometimes with pain
	 3 Yes, but always with pain
	 4 No
	 1 Yes, comfortably
11. Have you walked around the different rooms in your house or apartment?	 2 Yes, but sometimes with pain
	 3 Yes, but always with pain
	 4 No
	 1 Yes, comfortably
12. Have you walked from your bedroom to the bathroom?	 2 Yes, but sometimes with pain
	 3 Yes, but always with pain
	 4 No

Table 3. Component Items of the Satisfaction Scale

How satisfied are you with:			
13. The overall result of back treatment?			
 Very satisfied	 Somewhat satisfied	 Somewhat dissatisfied	 Very dissatisfied
14. Relief of pain following the treatment?			
 Very satisfied	 Somewhat satisfied	 Somewhat dissatisfied	 Very dissatisfied
15. Your ability to walk following the treatment?			
 Very satisfied	 Somewhat satisfied	 Somewhat dissatisfied	 Very dissatisfied
16. Your ability to do housework, yard work, or job following the treatment?			
 Very satisfied	 Somewhat satisfied	 Somewhat dissatisfied	 Very dissatisfied
17. Your strength in the things, legs, and feet?			
 Very satisfied	 Somewhat satisfied	 Somewhat dissatisfied	 Very dissatisfied
18. Your balance, or steadiness on your feet?			
 Very satisfied	 Somewhat satisfied	 Somewhat dissatisfied	 Very dissatisfied

Hospital Anxiety and Depression Scale (HADS)

Tick the box beside the reply that is closest to how you have been feeling in the past week. Don't take too long over your replies: your immediate is best.


1. I feel tense or "wound up":
 
3 Most of the time 2 A lot of the time 1 From time to time, occasionally 0 Not at all
 
2. I still enjoy the things I used to enjoy:
 
0 Definitely as much 1 Not quite so much 2 Only a little 3 Hardly at all
 
3. I get a sort of frightened feeling as if something awful is about to happen:
 
3 Very definitely and quite badly 2 Yes, but not too badly 1 A little, but it doesn't worry me 0 Not at all
 
4. I can laugh and see the funny side of things:
 
0 As much as I always could 1 Not quite so much now 2 Definitely not so much now 3 Not at all
 
5. Worrying thoughts go through my mind:
 
3 A great deal of the time 2 A lot of the time 1 From time to time, but not too often 0 Only occasionally
 
6. I feel cheerful:
 
3 Not at all 2 Not often 1 Sometimes 0 Most of the time
 
7. I can sit at ease and feel relaxed:
 
0 Definitely 1 Usually 2 Not Often 3 Not at all
	
8. I feel as if I am slowed down:
 
3 Nearly all the time 2 Very often 1 Sometimes 0 Not at all
 
9. I get a sort of frightened feeling like 'butterflies' in the stomach:
 
0 Not at all 1 Occasionally 2 Quite Often 3 Very Often
 
10. I have lost interest in my appearance:
 
3 Definitely 2 I don't take as much care as I should 1 I may not take quite as much care 0 I take just as much care as ever
 
11. I feel restless as I have to be on the move:
 
3 Very much indeed 2 Quite a lot 1 Not very much 0 Not at all
 
12. I look forward with enjoyment to things:
 
0 As much as I ever did 1 Rather less than I used to 2 Definitely less than I used to 3 Hardly at all
 
13. I get sudden feelings of panic:
 
3 Very often indeed 2 Quite often 1 Not very often 0 Not at all
 
14. I can enjoy a good book or radio or TV program:
 
0 Often 1 Sometimes 2 Not often 3 Very seldom

--	---

Expectation Assessment

In general, is acupuncture effective for controlling the illness?
 Yes
 No
 Unclear
Do you think acupuncture will be helpful to improve your DLSS symptoms
 Yes
 No
 Unclear

Efficacy of acupuncture for treatment of intermittent claudication in patients with degenerative lumbar spinal stenosis

Statistical Analysis Plan (SAP)

NCT number: NCT03784729

February 25, 2019

Content

1. Introduction.....	1
2. Study Objective.....	1
3. Design	1
3.1 Overview.....	1
3.2 Eligibility criteria	2
3.2.1 Inclusion Criteria.....	2
3.2.2 Exclusion Criteria.....	2
4. Schedule of Evaluation	3
5. Efficacy and Safety outcomes.....	4
5.1 Efficacy outcomes.....	4
5.1.1 Primary Outcome	4
5.1.2 Secondary Outcomes.....	4
5.2 Safety outcomes	4
6. Statistical Considerations.....	6
6.1 Study Hypothesis	6
6.2 Statistical Analysis Set	6
6.3 Statistical Analyses	6
6.3.1 The general principle.....	6
6.3.2 Demographics and Baseline Characteristics	6
6.3.3 Analysis for Primary Outcome	7
6.3.4 Analyses for Secondary Outcome	7
6.3.5 Safety Analyses	7
7. References.....	8

1. Introduction

Degenerative lumbar spinal stenosis (DLSS) is a condition involving narrowing of the space for the sagittal diameter of the spinal canal or nerve root canal for the spinal nerve or cauda equina secondary to degenerative changes [1-3]. DLSS is a common cause of gluteal and lower extremity pain and more likely to affect women and elderly people aged 60–70 years [4]. Because imaging evidence is not necessarily related to clinical symptoms, there are no specific epidemiological data for DLSS [5, 6]. According to the results of magnetic resonance imaging (MRI), 30–90% of asymptomatic adults may have spinal abnormalities including disc herniation, disc degeneration, or spinal stenosis [7]. DLSS is the most common type of spinal stenosis [1, 8]. The early symptoms of DLSS are soreness and pain in the low back, gluteal region, and posterior region of the thighs, which can be relieved after resting or changing posture. As patients with DLSS experience gradually aggravated symptoms, they may have neurogenic claudication with hypoesthesia and numbness in the lateral lower legs and feet; additionally, some patients may have bowel and bladder disturbances [9, 10]. DLSS patients have a poor quality of life, especially elderly patients [11]. In accordance with the guidelines of the North American Spine Society, treatment options comprise surgical therapy, epidural steroid injections and physical therapy, and transcutaneous electrical stimulation. According to some studies, the long-term efficacy of surgery is not superior to that of non-surgical therapy [12-15]. More studies are required to explore the efficacy of non-surgical therapy [16]. According to a systematic review [17] and recent studies [18, 19], acupuncture may improve the symptoms of patients and thus their quality of life; however, there is a lack of placebo-controlled and large-sample sized studies. More studies with a sufficient sample size are needed to provide evidence of the efficacy of acupuncture for treating DLSS.

2. Study Objective

The aim of this study is to assess the effects and safety of acupuncture for relieving predominantly neurogenic claudication pain in patients with central DLSS.

3. Design

